4.1.8 Drug accountability

The investigator or designee will receive the investigational drugs delivered by the sponsor when the following requirements are fulfilled:

- Approval of the clinical trial protocol by the institutional review board (IRB)
- Availability of a signed and dated clinical trial contract between the sponsor and the investigational site,
- Notification to the Pharmaceuticals and Medical Devices Agency,
- Availability of the curriculum vitae of the principal investigator,
- Availability of a signed and dated clinical trial protocol,

Investigational drugs are not allowed to be used outside the context of this protocol. They must not be forwarded to other investigators or clinics. Patients should be instructed to return unused investigational drug.

The investigator or designee must maintain records of the product's delivery to the trial site, the inventory at the site, the use by each patient, and the return to the sponsor or warehouse / drug distribution centre or alternative disposal of unused products. If applicable, the sponsor or warehouse / drug distribution centre will maintain records of the disposal.

These records will include dates, quantities, batch/serial numbers, expiry ('use- by') dates, and the unique code numbers assigned to the investigational medicinal product and trial

patients. The investigator or designee will maintain records that document adequately that the patients were provided the doses specified by the clinical trial protocol and reconcile all investigational medicinal products received from the sponsor. At the time of return to the sponsor or appointed CRO, the investigator or designee must verify that all unused or partially used drug supplies have been returned by the clinical trial patient and that no remaining supplies are in the investigator's possession.

4.2 OTHER TREATMENTS, EMERGENCY PROCEDURES, RESTRICTIONS

4.2.1 Other treatments and emergency procedures

Throughout the duration of the trial, patients should continue to take their previous antidiabetic therapy as permitted by trial protocol, including acceptable OADs with the exception of SGLT-2 inhibitors (treatment with insulin and GLP-1 agonists is excluded as well, see Section [4.2.2](#)). This background medication of OADs should remain unchanged throughout the study. The background medication will not be provided as part of the clinical trial supplies.

The patients can take their background medication as they are used to and should have the same habits of dosing throughout the trial. Morning dose of OADs and study medication should be taken after the visits blood samples are taken.

Hyperglycaemia

Rescue medication can be given if the criterion below is met during the run-in period at the investigator's discretion. Patients who need rescue medication prior to Visit 3 are not eligible for randomisation. Please see Section [3.3.4.1](#):

- The patient has a glucose level >200 mg/dL (>11.1 mmol/L) after an overnight fast

Rescue medication, for the treatment of hyperglycaemia, can be initiated during the double-blind treatment period of the trial (i.e., from Visit 3 to Visit 8) at the investigator's discretion if the criterion below is met:

- The patient has a glucose level >200 mg/dL (>11.1 mmol/L) after an overnight fast

The above results should be confirmed, meaning that there is a minimum of two measurements, at least second measurement should be performed at the investigational site after an overnight fast (central or local laboratory testing is allowed), and on a different day to the initial measurement.

In order to expedite the rescue medication initiation decision, the investigator may confirm the results (second measurement) at the local or commonly used laboratory. This procedure with its results should be documented in the patient's medical chart. Before initiation of rescue therapy a FPG sample should be drawn and sent to the central lab for analysis.

If the above criteria are met, the initiation of rescue medication is at the Investigator's discretion, based on the patients' current clinical condition (e.g., ongoing illness etc.). If dose of standard of care increase, it should be recognised as rescue medication.

Rescue medication can be used from when it is initiated until the end of the trial. The choice of rescue medication and its dosage will be left to the discretion of the investigator excluding SGLT-2 inhibitors. Regardless of the choice made, rescue medication should be taken in accordance with the prescribing information of that respective medication, taking into account potential contraindications.

In the case of hypoglycaemic event that may put patient on risk (e.g., repeated symptomatic hypoglycaemic events or severe hypoglycaemic event), appropriate adjustment of oral antidiabetic therapy such as a dose reduction/discontinuation of ongoing rescue medication should be initiated.

If, in the investigator's clinical opinion, no further effect from the rescue medication is anticipated, and the patient's hyper- or hypoglycaemia cannot be controlled, the patient should be discontinued from the trial as specified in Section [3.3.4](#).

Any rescue medications should be recorded in the source documents and on the appropriate pages of the eCRF.

Rescue medication will not be provided as part of the clinical trial supplies.

Special attention must be paid to the prevention of DKA. All patients must be made aware of this risk and need to be instructed to contact the investigator or other healthcare professional in case of symptoms of DKA.

In case of a suspected DKA the investigator should ensure that appropriate tests are performed at the earliest opportunity according to guidelines in Japan, such as a blood gas test (i.e., pH, bicarbonate, anion gap, potassium, blood glucose, etc; the results will be collected on the relevant page of the eCRF) and that the patient is appropriately treated (i.e., hospitalised or referred to emergency treatment) according to treatment guidelines in Japan.

Any additional treatment, that does not qualify as a rescue medication, and is considered necessary for the patient's welfare may be given at the discretion of the investigator. Exceptions to this are the restrictions described in Section [4.2.2](#).

There are no special emergency procedures to be followed.

4.2.2 **Restrictions**

4.2.2.1 Restrictions regarding concomitant treatment

Patient can continue any standard of care if patient used it before participating in the trial. Antidiabetic therapy has to be unchanged for 12 weeks prior to randomisation (for thiazolidinedione, therapy has to be unchanged for at least 18 weeks prior to informed consent).

SGLT-2 inhibitors (other than blinded study medication), Insulin, GLP-1 agonists, and any other diabetes drugs other than standard of care will be prohibited during the course of the trial.

Treatment with anti-obesity drugs or systemic steroids will be prohibited due to their influence on glucose metabolism and muscle mass. However, intermittent or short-term use (i.e., ≤ 2 weeks duration) of systemic steroids will be permitted as well as therapy with non-systemic steroids such as inhaled or local steroids. Furthermore, for patients taking thyroid hormones and testosterone, any change in the dose should be avoided. If dose changes do occur, then they should be recorded in the source documents and in the eCRF.

4.2.2.2 Restrictions on diet and life style

Through the clinical trial, patients will receive diet and exercise counselling by a diet specialist or trained trial staff. The counselling will be based on the diet and exercise recommendations of The Japanese Diabetes Society. The patients will be reminded to follow the agreed diet and exercise plan.

To avoid DKA, extreme diets (e.g., ketogenic diets) have to be avoided.

Through the double-blind treatment period, the investigator and trial staff will instruct the patient to drink appropriate volume of water every day. and it must be ensured particularly in the beginning of use of investigational drug, and caution must be continued during use.

Herbal or nutritional supplements with effect on blood glucose are prohibited throughout trial. Patients using/requiring these supplements should be discontinued from the trial, see Section [3.3.4.1](#).

Patients also should not take investigational drug in another trial within 30 days prior to Visit 1 in this trial. Furthermore, patients should not participate in another trial (involving an investigational drug) after discontinuing medication in this trial for the remaining trial period.

There are no other restrictions on diet and lifestyle.

4.2.2.3 Contraception requirements

Only male and post-menopausal female participate in this trial. Therefore, there are no special contraception requirements to be followed.

4.3 TREATMENT COMPLIANCE

Patients are requested to bring all remaining trial medication including empty package material with them when attending visits.

Based on tablet counts, treatment compliance will be calculated as shown in the formula below. Compliance will be verified by the CRA authorised by the sponsor.

$$\text{Treatment compliance (\%)} = \frac{\text{Number of tablet actually taken} \times 100}{\text{Number of tablet which should have been taken as directed by the investigator}}$$

Proprietary confidential information © 2020 Boehringer Ingelheim International GmbH or one or more of its affiliated companies

If the compliance is smaller than 80% or larger than 120%, site staff will explain a reason in eCRF and remind to the patient the importance of treatment compliance.

5. ASSESSMENTS

5.1 ASSESSMENT OF EFFICACY

5.1.1 HbA1c

HbA1c is considered appropriate to evaluate the efficacy as primary endpoint because HbA1c is an internationally accepted endpoint of stable glycaemic control.

Blood samples for the determination of HbA1c at the central laboratory will be taken at all the visits except Visit 2, the blood sample can be taken at any time during the visit. For the determination of HbA1c, 3 mL of blood will be collected. The samples will be analysed at a central laboratory having a National Glycohaemoglobin Standardisation Program (NGSP) Level I certificate. Further details about sample handling, shipment, and assay procedures can be found in the ISF (Lab manual).

5.1.2 Grip strength

Grip strength is an important function of upper extremities for elderly population, and it is used for the assessment of sarcopenia in AWGS 2019 [R20-0617]. The Sarcopenia Frail Society of Japan recommends to use this criterion of AWGS. Therefore, grip strength is a parameter to evaluate physical condition and assess sarcopenia.

The procedure to measure grip strength is described in Appendix [10.1](#).

5.1.3 Lower limb function

Lower limb function for elderly population is an important function, and it is used for the assessment of sarcopenia in AWGS 2019 [R20-0617]. The Sarcopenia Frail Society of Japan recommends to use this criterion of AWGS. As same as grip strength, time of chair stand test is a parameter to evaluate physical condition and assess sarcopenia.

The procedure to implement chair stand test is described in Appendix [10.2](#).

5.1.4 Body composition

Body composition assessment is being increasingly recognised as an important tool in the evaluation of nutritional status in a variety of clinical conditions and for fitness assessment in both research and clinical settings and muscle mass is an important parameter for diagnosing sarcopenia in AWGS 2019 [R20-0617].

Bioelectrical impedance analysis (BIA) is a commonly used method for estimating body composition and it assesses body composition by passing a very small current through the body and assessing differences in impedance caused by the fact that fat and lean tissues have different electrical properties. Since all lean tissue in the limbs is either bone or muscle use of segmental BIA can provide a good proxy for skeletal muscle mass by assessing the composition of limbs alone. BIA is a valid tool for the assessments of total body and

Proprietary confidential information © 2020 Boehringer Ingelheim International GmbH or one or more of its affiliated companies

segmental body composition in the general middle-aged population, particularly for the quantification of body lean mass [[R20-0698](#)].

The body composition planned to be measured by using BIA includes muscle mass (kg), body fat percentage (%), body fat mass (kg), lean body mass (fat-free mass) (kg), total body water (kg), and bone mineral content (estimated bone mass) (kg). Skeletal muscle index is calculated by dividing the limb muscle mass (kg) by the square of the height (m²). The procedure to measure body composition is described in Appendix [10.3](#) and instruction in ISF.

5.2

ASSESSMENT OF SAFETY

5.2.1 Physical examination

A complete physical examination will be performed at the time points specified in the [flowchart](#). It includes at a minimum general appearance, neck, lungs, cardiovascular system, abdomen, extremities, and skin.

Targeted physical examination will include evaluation of organ systems associated with AE(s) symptoms or laboratory abnormalities.

Measurement of height, calf circumference, and body weight will be performed at the time points specified in the [flowchart](#). For calf circumference, the maximum non-dominant calf circumference is measured.

The results must be included in the source documents available at the site.

5.2.2 Vital signs

Vital signs will be evaluated at the time points specified in the flowchart, prior to blood sampling. Clinically relevant abnormal findings as judged by the investigator will be reported as AE (see Section [5.2.6](#)).

Vital signs include systolic and diastolic blood pressure and pulse rate (electronically or by palpation count for 1 minute) in a seated position after 5 minutes of rest. The results must be included in the source documents available at the site.

5.2.3 Safety laboratory parameters

Safety laboratory parameters to be assessed are listed in Table [5.2.3: 1](#), [5.2.3: 2](#) and [5.2.3: 3](#). For the sampling time points please see the flowchart.

All analyses will be performed by a central laboratory, the respective reference ranges will be provided in the ISF.

Safety laboratory samples (except screening) will be collected after a full overnight fast (nothing to eat or drink except water for at least 10 hours) and before administration of background antidiabetic therapies and investigational drug as described in the flowchart and [Section 6](#). The blood sample at Visit 1 (screening visit) can be taken with the patient in a fasted or nonfasted state.

Instructions regarding sample collection, sample handling/ processing and sample shipping are provided in the ISF (lab manual).

It is the responsibility of the investigator to evaluate the laboratory reports. Clinically relevant abnormal findings as judged by the investigator will be reported as AE (please refer to Section [5.2.6](#)).

In case the criteria for hepatic injury are fulfilled, a number of additional measures will be performed (see Section [5.2.6.1](#) and the DILI checklist provided in the ISF). The amount of blood taken from the patient concerned will be increased due to this additional sampling.

The central laboratory will transfer the results of the analysis to the sponsor.

Table 5.2.3: 1

Safety laboratory tests – Haematology

Visit	1	2	3	4	5	6	7	8 EOT	9 EOS
Study week	-3	-2	0	4	12	24	36	52	53*
Haematocrit	X		X	X	X		X	X	X
Haemoglobin	X		X	X	X		X	X	X
Red Blood Cells (RBC)/Erythrocytes	X		X	X	X		X	X	X
WBC/Leukocytes	X							X	
Platelet Count/Thrombocytes	X							X	
Differential Automatic (relative and absolute count): Neutrophils, Eosinophils, Basophils, Monocytes, Lymphocytes	X							X	

* EOS should be done 1 week after Visit 8 or EOT

Table 5.2.3: 2

Safety laboratory parameters – Clinical Chemistry

Visit	1	2	3	4	5	6	7	8 EOT	9 EOS
Study week	-3	-2	0	4	12	24	36	52	53*
Glucose (fasted)	X	X	X	X	X		X	X	X
Lipase	X		X	X	X		X	X	X
AST (aspartate transaminase, SGOT)	X		X	X	X		X	X	X
ALT (alanine transaminase, SGPT)	X		X	X	X		X	X	X
Alkaline phosphatase	X		X	X	X		X	X	X
Bilirubin total	X		X	X	X		X	X	X
Direct bilirubin, if bilirubin total increased	X		X	X	X		X	X	X
Total Protein	X		X	X	X		X	X	X
Albumin	X		X	X	X		X	X	X
Potassium	X		X	X	X		X	X	X
Sodium	X		X	X	X		X	X	X
Bicarbonate	X		X	X	X		X	X	X
Creatinine	X		X	X	X		X	X	X
Blood urea nitrogen	X		X	X	X		X	X	X
Calcium	X		X						X
Inorganic phosphorous			X						X
Uric acid	X		X						X
Cholesterol (total)			X						X
HDL cholesterol			X						X
LDL cholesterol			X						X
Triglycerides			X						X
Thyroid stimulation hormone	X								

* EOS should be done 1 week after Visit 8 or EOT

Table 5.2.3: 3

Safety laboratory parameters – urine

Visit	1	2	3	4	5	6	7	8 EOT	9 EOS
Study week	-3	-2	0	4	12	24	36	52	53*
Protein	X		X	X	X		X	X	X
Ketone	X		X	X	X		X	X	X
Leucocytes	X		X	X	X		X	X	X
Erythrocytes	X		X	X	X		X	X	X

* EOS should be done 1 week after Visit 8 or EOT

If the investigator needs safety lab (e.g., to follow an ongoing AE), he/she can perform it in the local lab. The results will not be captured in the eCRF. Clinically significant lab abnormalities will be reported as AE (see Section [5.2.6](#)).

Estimate glomerular filtration rate

The estimated glomerular filtration rate (eGFR) will be derived from serum creatinine* values based on the standard MDRD formula:

$$\text{eGFR (ml/min/1.73 m}^2\text{)} = 175 \times [\text{Screatinine (umol/L)/88.4}]^{-1.154} \times [\text{age}]^{-0.203} \times [0.742 \text{ if patient is female}] \times [1.212 \text{ if patient is of African origin}]$$

*: creatinine methods calibrated to an IDMS reference method

NT-proBNP will be measured at screening as part of baseline examinations to characterise the patient population in the trial.

5.2.4 Electrocardiogram

The 12-lead electrocardiogram (ECG) must be administered by a qualified technologist and results will be recorded as scheduled in the [flowchart](#). The investigator or a designee will evaluate whether the ECG is normal or abnormal and assess clinical relevance. ECGs may be repeated for quality reasons and a repeated recording used for analysis.

Additional ECGs may be recorded for safety reasons. Dated and signed printouts of ECG with findings should be documented in patient's medical record.

Clinically relevant abnormal findings will be reported either as baseline condition (if identified at the screening visit) or otherwise as AEs and will be followed up and/or treated as medically appropriate.

5.2.5 Other safety parameters

Self-monitoring of blood glucose

All patients will be provided at Visit 2 with SMBG equipment and supplies for use at home throughout trial participation. Instruction on the proper use of the SMBG equipment will be provided by the trial staff. The patient will be asked to record the results of the SMBG test on a SMBG test log and will submit it to site staff at every visit. The log will be included in the

patients source document file. Clinically relevant abnormal findings as judged by the investigator will be reported as AE (see Section [5.2.6](#)). Only in the case of linked AEs or of hypoglycaemia events, the single SMBG values will be recorded in the eCRF.

During the run-in period, SMBG test is recommended to be done daily in the fasted state (before breakfast, i.e., after an overnight fast) and at any time the patient is symptomatic, i.e., experiences signs/symptoms of hyper- or hypoglycaemia. If during this period, results of a fasting SMBG test reveal blood glucose levels meeting rescue criteria (see Section [4.2.1](#)), the patient should contact the site and the investigator should follow the instructions given in Section 4.2.1. During the double-blind treatment period, SMBG test is recommended to be done daily but be performed at least once a week in the same way as in the run-in period.

For the 1 week follow-up period, after the Visit 8 (EOT) up to a time period as judged by the investigator, SMBG test should be performed at least once daily in the fasted state and any time the patient is symptomatic, i.e., experiences signs/symptoms of hyper- or hypoglycaemia. If result of SMBG test reveals blood glucose of >200 mg/dL (11.1 mmol/L) after an overnight fast the patient should contact the site to assess if a change in his/her T2DM treatment is required.

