5.2.6 Assessment of adverse events

5.2.6.1 Definitions of AEs

5.2.6.1.1 Adverse event

An AE is defined as any untoward medical occurrence in a patient or clinical investigation subject administered a medicinal product and which does not necessarily have to have a causal relationship with this treatment.

An AE can therefore be any unfavourable and unintended sign (including an abnormal laboratory finding), symptom, or disease temporally associated with the use of a medicinal product, whether or not considered related to the medicinal product.

The following should also be recorded as an AE in the CRF and BI SAE form (if applicable):

- Worsening of the underlying disease or of other pre-existing conditions
- Changes in vital signs, ECG, physical examination, data on SMBG log and laboratory test results, if they are judged clinically relevant by the investigator.

If such abnormalities already exist prior to trial inclusion, they will be considered as baseline conditions and should be collected in the eCRF only.

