7.8.1.3 Analysis of hypoglycaemic events

The investigator will record for each AE whether it represents a hypoglycaemic event and, if so, record additional information to assess the intensity of the hypoglycaemic event. On the basis of this information the hypoglycaemic event will be classified as:

- confirmed hypoglycaemic adverse event are defined as hypoglycaemic adverse events that had a glucose concentration ≤ 70 mg/dL or required assistance.
- severe hypoglycaemia: event requiring assistance.
- hypoglycaemia event with blood glucose level <54 mg/dL (<3.0 mmol/L), even if asymptomatic.
- symptomatic hypoglycaemia, independent of the blood glucose value (this includes cases when the blood glucose was not measured during the event, but hypoglycaemia was diagnosed based on the clinical presentation).

The number of patients with hypoglycaemia according to investigator's judgement will be tabulated by treatment group. A subgroup analysis of confirmed events with respect to age category, rescue therapy and renal function will be performed.

The impact of treatment on the occurrence of hypoglycaemia will be explored using logistic regression model involving treatment and continuous baseline HbA1c. Time to the onset of the first hypoglycaemia will be estimated by Kaplan-Meier method. The logistic regression and Kaplan-Meier analysis will be performed on confirmed events as for all hypoglycaemia tables.

Summaries of hypoglycaemic events will include total number of hypoglycaemic events, descriptive hypoglycaemic event rate, number of episodes per patient, severity and intensity of the worst episode, action taken, minimum glucose level of worst episode, and time to onset of first episode. Hypoglycaemic events will also be summarised by baseline eGFR using MDRD formula, background medication and age group.

Different tables will be shown for (i) patients with investigator defined asymptomatic or symptomatic hypoglycaemia reported as AE, (ii) patients with confirmed hypoglycaemic adverse events, i.e. hypoglycaemic adverse events that had a plasma glucose concentration ≤ 70 mg/dL or required assistance, and, (iii) patients with minor, confirmed hypoglycaemic adverse events, defined as a hypoglycaemic event that had a plasma glucose concentration ≤ 70 mg/dL but did not require assistance.

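### Low home glucose readings reach the database only when the investigator reports an event, so the SAP's glucose-defined hypoglycaemia classes can miss silent lows to a degree that depends on the site

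*Protocol*

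**What the plan says.** Protocol 5.2.5 gives every patient a home meter and a log. In the double-blind period "SMBG test is recommended to be done daily but be performed at least once a week", fasted, with extra tests when there are symptoms. The patient "will submit it to site staff at every visit", and the log is kept with the source documents. Two rules decide what leaves the log:

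- AE status: "Clinically relevant abnormal findings as judged by the investigator will be reported as AE". The AE definition in Protocol 5.2.6.1.1 repeats this, covering "data on SMBG log and laboratory test results, if they are judged clinically relevant by the investigator".
- Database entry: "Only in the case of linked AEs or of hypoglycaemia events, the single SMBG values will be recorded in the eCRF".

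The only SMBG threshold in the protocol is for high values (above 200 mg/dL). Hypoglycaemia is not among the AEs of special interest in Protocol 5.2.6.1.4.

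SAP 7.8.1.3 starts from AEs: "The investigator will record for each AE whether it represents a hypoglycaemic event". Flagged events are then put into classes, among them confirmed events (glucose of 70 mg/dL or lower, or assistance needed) and a "hypoglycaemia event with blood glucose level <54 mg/dL (<3.0 mmol/L), even if asymptomatic". The logistic regression and the Kaplan-Meier analysis use the confirmed class. SAP 6.6.3 does not replace missing safety data.

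**The concern.** A class that ignores symptoms is useful because it picks up lows that nobody felt. Those are the readings most likely to stay in the log, since nothing prompts a report except the investigator's view of relevance. Two sites could receive the same silent reading of 50 mg/dL, one reporting it and the other not, and both would be following the protocol.

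Hypoglycaemia is the first risk in the protocol's risk table (1.4.2), which notes a possible increase with sulfonylureas and glinides and names SMBG as part of the mitigation. Patients are 65 or older, and the entry criteria admit users of those drugs. About 128 patients over about 20 sites is roughly six per site (128 / 20 = 6.4), so differences in reporting habit can show in small counts. At stake are the absolute hypoglycaemia counts and the confirmed-event analyses built on them.

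**Working it through.** The documents state no expected hypoglycaemia rate, so there is no figure to reproduce. The main check follows one reading through the rules.

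**A silent fasting home reading of 50 mg/dL**
1. The patient writes it in the log and hands the log in at the next visit (Protocol 5.2.5).
2. It becomes an AE only if the investigator judges it clinically relevant (Protocol 5.2.5 and 5.2.6.1.1). No threshold settles this.
3. If it is not an AE, the remaining route to the eCRF is as a hypoglycaemia event. That term is undefined, so this route also depends on the site.
4. Even by that route, SAP 7.8.1.3 works from AEs flagged as hypoglycaemic. Without an AE, the reading is in neither the below-54 class nor the confirmed class.
5. Nothing later restores it, because safety data are not imputed (SAP 6.6.3).

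Some glucose reaches the sponsor by another path. Protocol Table 5.2.3: 2 schedules central-laboratory fasting glucose in the treatment period after randomisation at Weeks 4, 12, 36 and 52, and again at end of study. The central laboratory transfers these results, and SAP 7.8.2 summarises laboratory values against reference ranges. SAP 7.8.1.3 does not use them. Four treatment-period samples compare with about 52 (weekly) to 364 (daily, 52 x 7) planned home readings.

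**Illustration 1: incomplete reporting.** Inputs: 64 patients per arm (Protocol 7.5). Assumed, not in the documents: a proportion p with at least one silent value below 54 mg/dL, and a reporting probability r. Expected recorded patients = 64 x p x r.

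| p | r = 100% | r = 75% | r = 50% | r = 25% |
|---|---|---|---|---|
| 5% | 3.2 | 2.4 | 1.6 | 0.8 |
| 10% | 6.4 | 4.8 | 3.2 | 1.6 |

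**Illustration 2: effect on the comparison.** With assumed true proportions of 5% and 10% and a common r of 50%, the difference falls from 5 to 2.5 percentage points (10% x 0.5 - 5% x 0.5), while the ratio stays at 2. Equal under-recording shrinks absolute differences but does not reverse them.

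**Illustration 3: testing frequency.** With an assumed chance q that a fasting reading is below 54 mg/dL, independent between tests, the chance of seeing at least one low is 1 - (1 - q)^m.

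| q per test | m = 52 (weekly) | m = 364 (daily) |
|---|---|---|
| 0.05% | 2.6% | 16.6% |
| 0.1% | 5.1% | 30.5% |
| 0.2% | 9.9% | 51.7% |

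A count of lows therefore also depends on how often patients test, and better transcription would not change that.

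**The case against.** A reader might infer that the SAP contradicts itself or the protocol, because a reading of 50 mg/dL meets its definition yet cannot be counted. The text does not support this. SAP 7.8.1.3 classifies events already flagged by the investigator, and its first table is expressly for hypoglycaemia reported as an AE. The plan can be run as written. The issue is that a glucose-defined class suggests a threshold-based count, and the capture rule cannot deliver one.

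Other objections, and what stands of them:
- None of the three tables listed in SAP 7.8.1.3 is specific to values below 54 mg/dL, so no such table can be called wrong. The confirmed class has the same dependence, however, and it feeds the tables and both analyses.
- The target is AE-based, so an unreported reading lies outside it, and Protocol 7.2.5 calls the safety analysis descriptive. This is fair, and it makes the fix an added display and a label rather than a replacement.
- Central glucose already catches silent fasting lows at visits. This is true and should be used, but it covers only a few mornings.
- Sites see the logs, and entry instructions may sit in the investigator site file, which the protocol cites for eCRF questions. The flow chart and SAP 5.3 and 6.4 are not available here either. Uneven capture is therefore a risk that the visible rules allow, not a demonstrated fact.
- Requiring local laboratory glucose would conflict with Protocol 5.2.3, which keeps local results out of the eCRF. This is accepted, and the fix leaves them out.

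**Conclusion.** The point holds as a gap in ascertainment. Under the visible rules, recorded silent home lows can equal or fall below the number in the logs, and the shortfall depends on each site's judgement. It affects the confirmed class (70 mg/dL or lower) and the below-54 class. The direction is firm; the size is not. The 0.8 to 4.8 recorded patients against 3.2 to 6.4 rest wholly on assumed prevalence and reporting.

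A reader might infer that the treatment comparison of hypoglycaemia is biased towards one arm. The documents do not support that: investigators are blinded (Protocol 4.1.5.1), so under-recording should be similar in both arms on average. It lowers absolute counts and differences and adds noise between sites. The primary endpoint is unaffected. This is a worthwhile, inexpensive improvement, not a flaw that threatens the trial's main conclusion.

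**What to change.** - **Protocol 5.2.5 and the eCRF:** require every SMBG value of 70 mg/dL or lower (the SAP's own cut-off) from Visit 3 to 7 days after the last dose to be entered with date, value and symptoms yes/no, whether or not it is an AE. The 7 days match the AE window in Protocol 7.2.5 and SAP 7.8.1.1.
- **SAP 7.8.1.3, new display:** show patients per arm with any value of 70 mg/dL or lower and any value below 54 mg/dL, from these SMBG entries plus the central-laboratory glucose already transferred. Do not re-transcribe central values, and do not include local laboratory values. State the time window used, because SAP Table 6.7: 1 gives 7 days for AEs, 3 for safety laboratory values and 1 for FPG.
- **SAP 7.8.1.3, existing tables:** keep them and label them as investigator-reported events.
- **Testing intensity:** report the number of days with SMBG testing per arm, if collected, since testing may be daily or only weekly.

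The cost is one eCRF form, a few sentences in each document and some extra data entry from logs that sites already receive at every visit. The reported hypoglycaemia count may rise. The change concerns data capture and display only, not patient management.
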